9.3.1.2 Multiple measurements at one time point

All data will be included in the relevant listings.

For summary tables and figures, if two assessments are assigned to the same visit, the assessment closest to the target day for that window (see Section 9.5.1) will be used. Where two assessment dates are equidistant from the target visit date, the later assessment will be included for analysis.

9.3.1.3 Study day

The study day for assessment and event dates are derived from the date of first dose of the study drug (Day 1).

If the assessment/event date is before the date of first dose, then the study day is defined as:

$$(\text{Assessment/event date}) - (\text{Date of first dose})$$

If the assessment/event date is on or after the date of first dose, then the study day is defined as:

$$(\text{Assessment/event date}) - (\text{Date of first dose}) + 1$$

Missing assessment/event dates

Handling of partial or missing medical history, AE, prior medication, prior procedure, concomitant medication, and concomitant procedure dates is described below in the relevant derivation sections.

All other assessment/event dates should not be partial or missing. Querying should resolve missing dates prior to database lock. In the event of a partial or missing date at database lock, the assessment date will be imputed by visit date.

9.3.1.4 On-treatment

For patients that do not prematurely discontinue treatment, all post-baseline measurements on or before the end of the Week 48 window are considered on-treatment.

For patients that do prematurely discontinue treatment, only measurements that are taken whilst a patient is taking the study treatment will be on-treatment measurements. More specifically if:

$$(\text{Assessment date}) - (\text{Date of first dose}) + 1 > 0; \text{ and} \\ (\text{Date of last dose}) + 2 - (\text{Assessment date}) \geq 0$$

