10.3.6 Vital signs and physical examination

Patient's vital signs (pulse rate, respiration rate, systolic blood pressure, diastolic blood pressure and temperature) will be presented as follows:

For each timepoint (baseline, weeks 4, 12, 24, 36 and 48, and the safety follow-up visit) absolute values and change from baseline will be summarized with standard summary statistics (see Section 8.1), by

REACH TRIAL

treatment group. Weight will be presented in a similar way, but only at baseline, weeks 24 and 48, and the safety follow-up visit.

An on-treatment summary of vital signs will be presented. A low category and one or two high categories are pre-specified as follows:

Vital Signs Parameter	Low category	High Categories
Systolic blood pressure (mmHg)	< 90	> 140 to \leq 160 > 160
Diastolic blood pressure (mmHg)	< 50	> 90 to \leq 100 > 100
Pulse rate (bpm)	< 60	> 100
Temperature (°C)	< 36.0	> 38.0
Respiratory rate (breaths/min)	< 12	> 20
Body weight	\geq 7% decrease from baseline while on-treatment	\geq 7% increase from baseline

For each measurement type the number and percentage of patients: in each category at baseline (except body weight); with minimum on-treatment measurement in the lowest category; and with maximum on-treatment measurement in the highest category/categories will be presented.

All vital signs data will be presented by patient in a listing, by FSHD type and treatment group.

All physical examination data will be presented by patient in a listing, by FSHD type and treatment group.

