10.3.7 Electrocardiogram (ECG)

Each patient's maximum on-treatment QTcF interval will be categorized as \leq 450, > 450 to \leq 480, > 480 to \leq 500, > 500. The number and percentage of patients in each category will be presented by treatment group. Each patient's maximum on-treatment change from baseline in QTcF interval will be categorized as < 0, \geq 0 to \leq 30, > 30 to \leq 60, > 60. The number and percentage of patients in each category will be presented by treatment group.

All ECG data will be presented by patient in a listing, by FSHD type and treatment group

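### The on-treatment date formula for patients who stop drug early admits Day 1, so a same-day pre-dose Baseline ECG or vital sign can be reported as an on-treatment extreme

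*SAP*

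**What the plan says.** SAP 9.3.1.4 defines on-treatment separately for two groups.

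- **Patients who do not discontinue early:** "all post-baseline measurements on or before the end of the Week 48 window are considered on-treatment". Baseline is excluded by the wording.
- **Patients who discontinue early:** "only measurements that are taken whilst a patient is taking the study treatment will be on-treatment measurements". The section then makes this specific with two date conditions: (assessment date − first dose date + 1) > 0, and (last dose date + 2 − assessment date) ≥ 0. Neither condition mentions Baseline or time of day.

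Two safety sections use the flag.

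- SAP 10.3.6: "An on-treatment summary of vital signs will be presented". For each parameter it counts patients by their minimum and maximum on-treatment value, beside a count by category at baseline.
- SAP 10.3.7 categorises each patient's maximum on-treatment QTcF, and adds: "Each patient's maximum on-treatment change from baseline in QTcF interval will be categorized as" one of four bands, the lowest being below 0.

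Neither section removes Baseline records.

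**The concern.** The formula is what a programmer will code, and it does not do what its lead-in sentence says. A reading taken before any drug can enter a table labelled on-treatment, but only for patients who stopped early. The same reading in a patient who stayed on drug is excluded. The two groups are thus summarised under different rules in one table.

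These are per-patient extremes, so a single extra record can decide the category. A raised pre-dose blood pressure or QTcF could appear both as the baseline category and as an on-treatment finding. If more patients stop early in one arm, more pre-dose readings enter that arm's column. The QTcF table will be read with care, because protocol 1.3.5.2 reports that the primary analysis of the thorough QT study crossed the 10 msec threshold.

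**Working it through.** No published figure bears on this point, so the check evaluates the two date conditions and traces which records they admit.

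**Inputs**

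- Day 1 is the date of first dose. SAP 9.3.1.3: "The study day for assessment and event dates are derived from the date of first dose of the study drug (Day 1").
- The baseline visit is also called Day 1 (SAP 8.2; protocol 5.1.1).
- ECG, vital signs and drug dispensation are scheduled at Baseline, Study Day 1. The next scheduled ECG and vital signs are at Week 4, Study Day 28 (protocol Table 7; SAP Appendix B).
- The baseline value is the last non-missing value before first dose (SAP 9.2).

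**Evaluating the discontinuer formula**

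Let A be the assessment date, F the first dose date and L the last dose date. The example uses L = F + 60 days.

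| Assessment date | A − F + 1 | > 0? | L + 2 − A | ≥ 0? | On-treatment? |
|---|---|---|---|---|---|
| F − 1 | 0 | no | 63 | yes | no |
| F (Day 1) | 1 | yes | 62 | yes | **yes** |
| F + 1 | 2 | yes | 61 | yes | yes |
| L + 2 | 63 | yes | 0 | yes | yes |
| L + 3 | 64 | yes | −1 | no | no |

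A Baseline ECG taken on date F before the first tablet is flagged on-treatment for a discontinuer. For any other patient it is not post-baseline, so it is not flagged.

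**When the pre-dose value is the reported extreme**

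Suppose a discontinuer has k genuine on-treatment readings. As an illustration, assume no drug effect and exchangeable readings without ties. The pre-dose reading is then the maximum (or, equally, the minimum) of k + 1 readings with probability 1/(k + 1):

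| k | 0 | 1 | 2 | 3 | 4 |
|---|---|---|---|---|---|
| Probability | 100% | 50% | 33% | 25% | 20% |

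The case k = 0 needs no assumption. A patient who stops before Week 4, and whose next ECG is more than 2 days after the last dose, has only the pre-dose value. Protocol 4.3.2 allows for an early termination visit more than 7 days after the last dose, so this can happen.

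These probabilities concern which reading is selected. A table cell changes only when the pre-dose reading lies in a more extreme category than every later on-treatment reading, or when there is no later one.

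**Checking the correction**

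A date-only change to A − F + 1 > 1 would exclude Day 1 (1 > 1 is false), but it would also drop a genuine post-dose reading on Day 1. Requiring the record to be post-baseline removes the pre-dose reading without that loss.

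**The case against.** The strongest reply is that the intent is plain. The lead-in sentence limits the flag to time on drug, SAP 10.3.6 tabulates baseline categories separately, and SAP 9.5.1 gives Baseline its own window. On that reading the inequalities only set calendar limits. This stands as evidence of intent, but the inequalities are offered as the specific form of the rule, and they admit what the sentence excludes. Where prose and formula conflict, one has to be corrected.

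Second, the effect needs the first dose and the Baseline assessment on the same calendar date. The Day 1 convention implies this, but no section requires the first dose to be taken in clinic at the Baseline visit. Protocol 5.1.2 asks for in-clinic dosing only at PK visits. A patient who first doses the next day gives 0 > 0, which is false, and is unaffected. This condition stands.

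Third, the QTcF effect is limited. Screening excludes QTcF above 450 msec in men and 470 msec in women, so a pre-dose value would seldom create an entry above 480 msec. This also stands. It does not cover vital signs, because the eligibility criteria set no blood pressure or pulse limit.

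A reader might infer two stronger things.

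- **That a discontinuer's maximum QTcF change can never be below 0.** This would need a change of 0 to be derived for the Baseline record. SAP 9.2 computes change from post-treatment values, so it does not call for one.
- **That about 23 patients are affected, from 10% × 230.** The 10% in SAP section 5 is assumed missing Week 48 data, not a rate of stopping drug. Patients who stop drug are encouraged to stay in the study (SAP 9.1), so the two rates need not agree.

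**Conclusion.** Wrong as written, low severity. For early discontinuers whose first dose is on the date of the Baseline visit, the SAP 9.3.1.4 formula flags pre-dose Baseline ECGs and vital signs as on-treatment. The rule for other patients does not, and the section's own prose points the other way.

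The conclusion is firm for the maximum QTcF categories in SAP 10.3.7 and the minimum and maximum vital-sign categories in SAP 10.3.6. It does not extend to the QTcF-change bands unless a zero change is created for Baseline. It does not extend to the 7% body-weight categories either, since a change of 0 falls in neither.

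The number of patients affected cannot be derived. It depends on how many stop early, how many first dose on the Baseline date, and how many on-treatment readings they have.

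The primary analysis, the alpha-controlled secondary analyses and Sensitivity Analysis 1 are unaffected, because they use post-baseline values.

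**What to change.** In SAP 9.3.1.4, replace the first date condition for early discontinuers with a requirement that the measurement is post-baseline, meaning taken after the baseline record defined in SAP 9.2. Keep the upper limit of 2 days after the last dose. Both groups then share the same post-baseline condition and differ only in where the period ends.

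Prefer this wording to a study-day cut-off above 1, which would discard a true post-dose reading on Day 1. Because SAP 9.2 foresees Day 1 assessments without a recorded time, add a short note on how an untimed Day 1 record that is not the baseline record is handled. Such records should be few, since the schedule has no separate post-dose ECG or vital signs on Day 1.

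The cost is a small change to the SAP text and the matching change in the derivation program. Data collection and the efficacy analyses are not touched. Patients left with no on-treatment reading should appear as having none.

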9.3.1.5 MRI data

The objectives of the study relate to whole body longitudinal composite MFI and MFF. In addition, exploratory analyses are planned for whole body longitudinal composite lean muscle volume (LMV); analysis of each muscle MFI, MFF and LMV; and RWS cross-sectional composite MFI, MFF and LMV. MRI data are complex, and an intermediate step of derivation is carried out prior to statistical analysis. Derivations for this intermediate step may be found in Appendix C. The section below gives derivations relevant to the statistical analysis using the dataset that will be analyzed. These derivations are common to MFI, MFF and LMV endpoints.

Muscle categories

A, B, C muscle category codes are assigned to each muscle at baseline by the MRI vendor based on MFF and MFI and are applied throughout the study:

MFF Criteria		MFI criteria	Muscle Category	Code
MFF < 50%	and	MFI < 10%	Normal	A
MFF < 50%	and	MFI \geq 10%	Affected	B
MFF \geq 50%	-	-	End-stage	C

REACH TRIAL

where:

- A. Normal = a muscle that appears normal and is most likely not affected by disease.
- B. Affected = a muscle that is more likely to have disease involvement, but which still retains some functional capacity.
- C. End-stage = a muscle that is most likely to have loss of functional capacity.

Whole-body Longitudinal composite endpoints

These endpoints relate to measurements of change from baseline in LMV, MFI and MFF. These are specific to three muscle group categorizations: A, B, A+B. Note that baseline is measured during screening. If there is more than one screening measurement, then the last available assessment prior to first dose of treatment should be used. For the analysis of these endpoints four measures are required:

(1) Baseline whole body longitudinal LMV, MFI and MFF are variables with the label of type:

Lngrdl [Y] Ref Scrn [*Muscle categories included*] [*unit*]

where *Y*=MFI, MFF or LMV; *unit* = percentage points(pp) when *Y*=MFI or MFF; and *Muscle category included* = A, B, or A+B; and *unit* = liters (L) when *Y*=LMV; with Visit Name = 'Screening'.

(2) Change from baseline whole body longitudinal LMV, MFI and MFF are variables with the label of type:

Lngrdl [Y] Chng from Scrn [*Muscle categories included*] [*unit*]

where *Y*=MFI, MFF or LMV; *unit* = percentage points(pp) when *Y*=MFI or MFF; and *Muscle category included* = A, B, or A+B; and *unit* = liters (L) when *Y*=LMV; with Visit Name = '24 weeks' or '48 weeks'.

Change from baseline validity: At weeks 24 and 48, reference LMV is assessed using reference screening LMV ($LMV(t)_{REF}$); and reference screening muscle count ($N(t)_{REF}$), where $t=24$ or 48 . $N(t)_{REF}$ is the total number of individual muscles assessed at time t . These are labelled in the raw data as:

Lngrdnl LMV Ref Scrn [*Muscle categories included*]

Lngrdnl LMV Ref Scrn Mscl Cnt [*Muscle categories included*]

If a patient's reference LMV is too small, then change from baseline should be coded as missing per instruction from the MRI vendor. $LMV(t)_{REF}$ is considered too small if:

- $LMV(t)_{REF} < 0.25L$ when $N(t)_{REF} \geq 2$; or
- $LMV(t)_{REF} < 0.5L$ when $N(t)_{REF} = 1$

(3) Reference screening whole body longitudinal LMV, MFI and MFF for a muscle group are measured at weeks 24 and 48. These are labelled:

Lngrdnl [Y] Ref Scrn [*Muscle categories included*]

REACH TRIAL

where *unit* = percentage points(pp) when $Y=MFI$ or MFF ; and *unit* = liters (L) when $Y=LMV$.

(4) Absolute whole body longitudinal LMV, MFI and MFF for a muscle group measured at weeks 24 and 48 are derived from Reference screening and Change from baseline as:

Absolute for Y = Reference screening for Y at time t + Change from baseline for Y at time t
where $Y=MFI$, MFF or LMV , and $t=24$ or 48 weeks.

Individual muscle measurements

There are 36 muscles measured, 18 on each side of the body:

- Infraspinatus
- Subscapularis
- Supraspinatus
- Teres Minor
- Biceps Brachii
- Deltoideus
- Triceps Brachii
- Latissimus
- Dorsi/Teres Major
- Pectoralis Major
- Rhomboideus
- Serratus Anterior
- Spinal Erectors
- Th1-Sacrum
- Trapezius
- Adductors
- Gastrocnemius
- Medialis
- Hamstrings
- Quadriceps
- Tibialis

LMV, MFI and MFF are measured for each muscle at screening, 24 and 48 weeks. These are labelled as:

[Muscle Name] [measurement Type] [Unit of Measurement]

E.g., "Left Infraspinatus Muscle Fat Fraction (MFF) [%]."

Change from baseline is derived at 24 and 48 weeks as defined in 9.2 above.

Missing data

All MRI missing data where a scan is known to have taken place will be queried prior to database lock. For signal quality issues, see Appendix C.

9.3.2 Study population

Analysis populations are defined in Section 6.

9.3.2.1 Patient disposition

The total number of patients screened is the total number of unique patients recorded in the consent forms. These forms also define the total number of patients who gave informed consent.

Patients who consent but are ineligible are recorded in the Inclusion/Exclusion criteria form.

9.3.2.2 Demographics and baseline characteristics

Demographics and baseline characteristics are recorded in the following eCRF forms: Demographic Data; Height, Weight and BMI; FSHD History; and [REDACTED]. Most of these data are collected at screening. Weight is measured at screening and baseline: the measure taken closest to day 1 should be used.

9.3.2.3 Medical history

Medical history is recorded in the Relevant Medical History form of the eCRF. Partial or missing dates will not be imputed.

9.3.2.4 Concomitant medications/procedures

All medications or procedures used within 28 days prior to the date of screening through safety follow-up will be collected on the CRF (case report form). All medications will be coded according to the World Health Organization Drug Dictionary (WHODD Global B3 Mar 2019 or higher).

A prior medication or procedure is defined as any medication or procedure that is taken prior to the first dose of study drug regardless of when the medication or procedure ended. A concomitant medication or procedure is defined as any medication or procedure continued or newly received on or after the date of first dose of the study drug.

For the purpose of inclusion in prior and/or concomitant medication tables, incomplete medication start and stop dates will be imputed as follows:

- Medications with missing or partially missing start dates will have 2000 imputed for the missing year, January for the missing month, and 1 for the missing day.
- Medications with missing or partially missing stop dates will have 2050 imputed for the missing year, December for the missing month, and the last day of the month for the missing day.

For the purpose of listings, missing date data will not be imputed. For example, a date with a missing day but known to be in October 2023 will be presented as ??/OCT/2023. Where medications or procedures are ongoing, a stop date will not be presented.

9.3.2.5 Treatment exposure and compliance

The following will be derived from data collected in the Study Drug Accountability form of the eCRF:

For each visit post baseline:

- Number of tablets taken = Number of tablets dispensed at previous visit – Number of tablets returned for the visit
- Duration = (date of last dose) – (date of first dose) + 1.
- Tablets Prescribed = Duration x 2
- Study drug compliance (%) = $100 \times (\text{Number of tablets taken}) / (\text{Number of tablets prescribed})$

For the whole study:

- Treatment Duration = (Date of last dose) – (Date of first dose) + 1
- Cumulative dose is the total number of tablets taken across all study days times 15 mg
- Average daily dose is the cumulative dose divided by the total treatment duration
- Total number of tablets taken = Sum of numbers of tablets taken over all visits
- Total number of tablets prescribed = Sum of tablets prescribed over all visits
- Overall study drug compliance (%) = $100 \times (\text{Total number of tablets taken}) / (\text{Total number of tablets prescribed})$

If “Number of tablets returned” is missing, the Number of tablets returned will be assumed to be 0 in the calculations of treatment exposure and compliance but will be presented as missing in the listings.

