5.4.2. Study Drug Accountability

During the study, each patient will be provided a sufficient quantity of study drug to allow for dosing until their next scheduled visit plus additional tablets to cover the visit window. If needed, patients may be provided additional study drug via a courier service, as applicable. At the next scheduled clinic visit, patients must return their bottles of study drug for accountability.

The Investigator will maintain accurate records of receipt of all study drug, including dates of receipt. In addition, accurate records will be kept regarding when and how much study drug is dispensed and used by each patient in the study. Reasons for departure from the expected dispensing regimen must also be recorded. At the completion of the study, to satisfy regulatory

requirements regarding drug accountability, all study drug will be reconciled and retained or destroyed according to applicable regulations.

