10.1.6 Treatment exposure and compliance

Exposure and study drug accountability (compliance) will be presented for patients in the Safety Analysis Set.

Study drug exposure

Descriptive statistics will be used to summarize duration of exposure both as a continuous measure in days and weeks and by category: < 8 weeks, \geq 8 weeks, \geq 16 weeks, \geq 24 weeks, \geq 36 weeks, \geq 48 weeks, average daily dose, and cumulative dose.

Study drug accountability

Descriptive statistics will be used to summarize compliance as a continuous measure, and by category: < 80%, 80-120%, \geq 120%. Drug accountability will be presented in a listing, presented by FSHD type, treatment, and patient. For each patient, first dose date, last dose date, and treatment duration will be presented; and at each time-point, for dispensed study drug: bottle number, date and study day tablets were dispensed, and number of tablets dispensed; for returned study drug: date returned, number of tablets returned. The following treatment compliance data will be presented: Number of tablets taken, number of tablets prescribed, duration, and compliance.

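### The SAP's tablets-taken formula has no term for couriered drug, so recorded compliance and dose can be understated for patients supplied that way

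*SAP*

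**What the plan says.** For each post-baseline visit, SAP 9.3.2.5 defines: "Number of tablets taken = Number of tablets dispensed at previous visit – Number of tablets returned for the visit". The only supply that enters this count is therefore the "Number of tablets dispensed at previous visit". The denominator is "Tablets Prescribed = Duration x 2". The per-visit counts then feed the whole-study figures:

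- "Total number of tablets taken = Sum of numbers of tablets taken over all visits"; overall compliance divides this by the total prescribed.
- "Cumulative dose is the total number of tablets taken across all study days times 15 mg".
- The daily average spreads that amount over the days on treatment.

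The source is the Study Drug Accountability form of the eCRF. A missing return count is set to 0.

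Protocol 5.4.1 and 5.4.2 both say: "If needed, patients may be provided additional study drug via a courier service, as applicable". Section 5.4.2 adds that routine supply covers the time to the next visit plus the visit window, and that bottles come back at the next clinic visit.

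SAP 10.1.6 states: "Descriptive statistics will be used to summarize compliance as a continuous measure, and by category". The categories are below 80%, 80–120%, and 120% or more. The patient listing also shows tablets taken, tablets prescribed and compliance.

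**The concern.** The protocol permits two supply routes and the SAP formula names one. Read as written, a courier shipment is missing from the dispensed term, while any leftovers from it are inside the returned term. Both effects push the count down, and because the per-visit counts are summed, the whole-study figures carry the error.

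At stake is the record of whether treatment was delivered. Protocol 5.7 makes clinic tablet counts the compliance measure; diaries are optional. A patient who needed a courier, for example after a missed or delayed visit, is one whose adherence a reader of the study report would look at closely, and that patient's figure is the one exposed to the error.

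**Working it through.** The plan states no figure on this point, so there is none to reproduce. The check applies the SAP 9.3.2.5 formulas directly.

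**Inputs**

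- Visit days 28, 84, 168, 252 and 336 (Protocol Table 7), giving intervals of 28, 56, 84, 84 and 84 days.
- Two tablets a day (SAP 9.3.2.5): 56, 112, 168, 168 and 168 tablets prescribed, 672 in total over 336 days.
- 15 mg per tablet, so full adherence is 30 mg/day.
- Visit window ±7 days (Protocol Table 7, SAP 9.5.1).
- Assumptions: each supply is the interval plus 7 days (14 spare tablets), and the patient takes every dose. Courier quantities are varied because the documents give none.

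**Baseline check, no courier.** Week 12 to 24: (182 − 14)/168 = 100%. The other intervals also give 100%.

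**General form.** Let D be clinic tablets, C couriered tablets, R all tablets returned and L tablets lost.

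- True number taken: D + C − R − L.
- SAP count, if the shipment is not logged under a visit: D − R.
- Understatement: C − L. With no losses it equals the whole shipment, whether taken or returned.

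**Couriered tablets all taken, 336-day study**

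| Days' supply uncounted | Tablets | Overall compliance | Average daily dose |
|---|---|---|---|
| 7 | 14 | 658/672 = 97.9% | 29.4 mg |
| 14 | 28 | 644/672 = 95.8% | 28.8 mg |
| 28 | 56 | 616/672 = 91.7% | 27.5 mg |
| 84 | 168 | 504/672 = 75.0% | 22.5 mg |

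**What it takes to fall below 80%.** Overall: more than 0.2 × 672 = 134.4 tablets, about 67 days. Within one 84-day interval: more than 0.2 × 168 = 33.6 tablets, about 17 days. Within the 28-day interval: more than 0.2 × 56 = 11.2 tablets, about 6 days.

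**Short top-up.** A visit is 14 days late and 28 tablets are couriered. The interval is 98 days, 196 tablets are prescribed, and 182 + 28 − 196 = 14 are returned. SAP count: 182 − 14 = 168, so 168/196 = 85.7% for the interval and 672/700 = 96.0% overall.

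**Unused shipment.** 56 couriered tablets come back untouched in an 84-day interval: (182 − 14 − 56)/168 = 66.7% for the interval, 616/672 = 91.7% overall.

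**Missed dispensing visit.** Week 12 is missed.

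- Week 4 supply: (56 + 7) × 2 = 126. Courier: (84 + 7) × 2 = 182.
- Doses from Day 28 to Day 168: 140 × 2 = 280, all taken. Returned: 126 + 182 − 280 = 28.
- SAP count: 126 − 28 = 98, so 98/280 = 35.0% for the interval.
- Whole study: 672 − 182 = 490, so 490/672 = 72.9%, and 490 × 15/336 = 21.9 mg/day.

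If the missed visit is instead kept as a row with nothing dispensed, the Week 24 row is 0 − 28 = −28 tablets. A missed Week 24 visit with 182 tablets couriered gives the same 72.9% and 21.9 mg/day overall, with (182 − 28)/336 = 45.8% for its interval.

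**Counting both routes.** Late visit: (182 + 28 − 14)/196 = 100%. Missed Week 12: (126 + 182 − 28)/280 = 100%.

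**The case against.** The strongest reply is that the large figures depend on how the shipment is recorded, and the accountability form is not among the documents. A shipment that stands in for the Week 12 dispensation could naturally be entered under Week 12. The SAP's own rules then give 126 − 0 = 126 at Week 12, the missing return being set to 0 (126/112 = 112.5%), and 182 − 28 = 154 at Week 24 (154/168 = 91.7%). Together that is 280 of 280, or 100%, and 30 mg/day over the study. In addition, routine supply already covers the visit window, so couriers are an exception. The planned listing shows dispensing dates and quantities, so an unmatched shipment could be noticed. Diaries may also be used.

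A second reply is that courier drug may replace lost tablets. Suppose a 182-tablet bottle is lost halfway through an 84-day interval, after 84 tablets. The site couriers 98 and 14 come back. The SAP count is 182 − 14 = 168, exactly right, because the shipment and the loss cancel (C = L = 98). If that return count is missing, the result is 182/168 = 108.3%, too high rather than too low.

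Most of this stands as a limit on size and certainty. It does not rescue the rule. The SAP does not tell the programmer to assign a shipment to a visit, and a top-up sent within an interval replaces no visit's dispensation.

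**Conclusion.** The formula is wrong as written for a supply route that the protocol allows. Unless a shipment is logged under a visit, the count falls short by the number of couriered tablets taken or returned, net of any tablets lost. Short top-ups move overall compliance by a few points; a shipment the size of a full dispensation can move a fully adherent patient to 72.9%.

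Three stronger readings are tempting, and the documents support none of them.

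- A reader might infer that any adherent patient supplied by courier is scored non-compliant. Overall, that needs more than about 67 days of uncounted supply, although a single interval can fall below 80% much sooner.
- A reader might infer uneven distortion across sites or countries. The documents give no courier frequency, overall or by site.
- A reader might infer an effect on the efficacy result. None of the analysis sets in SAP section 6 uses compliance, the on-treatment definition in SAP 9.3.1.4 rests on dose dates, and compliance is only summarized and listed.

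The quantities rest on an assumed 7-day surplus, perfect adherence and chosen shipment sizes. This is a small correction to descriptive exposure and compliance tables.

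**What to change.** In SAP 9.3.2.5, define tablets taken as all tablets dispensed since the previous accountability visit, by clinic and by courier, minus all tablets returned from those dispensations. Use the same total for overall compliance, cumulative dose and average daily dose.

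Confirm that the Study Drug Accountability form captures courier shipments with date and quantity. If it does not, take them from the IRT or from the site dispensing records that Protocol 5.4.2 requires.

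State also that tablets documented as lost are not counted as taken. Without that line, the lost-bottle example would become (182 + 98 − 14)/168 = 158.3% under the new definition.

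The cost is a line or two of SAP text, minor programming and some reconciliation of dispensing records before database lock. Results for patients with no courier supply and no documented losses do not change.
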